|--|--|

| | |
|------------------------------------|---|
| | 
 - Carbon footprint of the intervention or carbon-saving due to the intervention |
| Procedures and measurements | 
Objective 1: Improve the integrated management of sick children
 
In Phase 1, in each region, after a pilot period of 6 months to test all the e-tools, eligible HFs will be randomized (by Region and HF) to the intervention or control arm. Sick children will be enrolled over a period of 6 to 9 months.
 
Primary outcome measures: (i) For assessing clinical cure at Day 7, a simple questionnaire (asking if the child is still sick, was hospitalized secondarily, or died) will be administered to all caregivers by phone; (ii) For measuring antibiotics prescribed at initial consultation, the treatment data recorded in the tablets or PCs by HCWs throughout the study will be compared between intervention and control arms.
 
Secondary outcome measures: To determine the quality of the consultation made by CHWs, including the rational use of antimicrobials (antibiotics and antimalarials), two sources of data will be used and compared between intervention and control arms:
 
 - the final decision on referral, tests performed, final diagnoses retained and treatment prescribed will be recorded in the tablets or PCs by HCWs at initial consultations and re-attendance visits. - during a cross-sectional survey, observers in the consultation room will record key symptoms and signs assessed by HCWs, diagnostic tests requested, final decision on referral, final diagnoses retained and treatment prescribed. 
Control arm: In control PHC facilities, sick children will be assessed, diagnosed and treated as per routine protocols by clinicians. A similar but simplified tablet or PC application will also be used in control facilities, but only to record outcome measure related data using an electronic case report form. HCWs in control facilities will be offered the usual training and supervision proposed by the CHMT.
 
In Phase 2, all selected HFs in the two regions will receive the intervention. Indicators monitored over time and across geographical areas will be measured the same way as in Phase 1, except that clinical cure, secondary hospitalizations and deaths may or may not be assessed through a phone call or an automated SMS or call to caregivers using the same simple questionnaire.
 
Objective 2: Improve the algorithm and adapt it to spatiotemporal variations
 
The algorithm will be improved in terms of diagnostic and prognostic accuracy and adapted to local fluctuations in epidemiology, demography, geography and resource availability. These modifications will be designed and supervised by clinical experts, based on accumulated data captured during the study in real-time and analyzed, including by ML when necessary. All modifications will first be tested on retrospectively collected data. If these analyses confirm an expected positive impact, the change in the algorithm will be implemented and its impact will be monitored through the continuous analysis of data looking at the related outcome indicators. For major modifications in the algorithm, a formal randomized sub-study will be conducted to assess precisely the potential benefit (or harm) on clinical outcome or non-inferiority. HCWs attending a child who could potentially benefit from this modification will be informed about the change in the algorithm. Either the modified branch or the standard branch of the algorithm will then appear on the screen to guide the HCW's decisions. Antimicrobial prescriptions, clinical cure and other outcomes related to the expected impact will be assessed the same way as in Phase 1 and compared between children managed with the new and the standard version of ePOCT+. If the positive impact is confirmed by the sub-study, the new algorithm branch will be implemented for all relevant children in the relevant HFs. Minor modifications in the algorithm (e.g. adding a non-critical symptom such as myalgia, or a slight modification of threshold of a laboratory test) will be implemented without sub-study, but some outcome indicators may be monitored.
 
Objective 3: Enhance disease surveillance and outbreak detection
 
All data generated by ePOCT+ will be sent to a central sever based at IHI. Data will be visualized through the medAL-outbreak dashboard made available to district health authorities using the key indicators they will have chosen. To enhance disease
 |

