These measures or indicators include the evaluation of the effects of the use of ePOCT+ (versus routine care in Phase 1; over time and across geographical areas in Phase 2) for managing sick children aged under 15 years presenting to PHC facilities on:

Unscheduled secondary consultations:

- % of children with one or more unscheduled re-attendance visits at any HF by day 7

Severe outcome by day 7:

- % of children with non-referred secondary hospitalization by day 7
- % of children who have died by day 7

Primary referrals:

- % of children referred to hospital or admitted to inpatient ward at a health centre at initial consultation
- % of children who were hospitalized among those referred (i.e. referral completed)

Appropriate case management for malaria at initial consultation

- % of febrile children tested for malaria
- % of malaria positive children prescribed an antimalarial
- % of malaria negative children prescribed an antimalarial
- % of untested children prescribed an antimalarial

Appropriate case management for other conditions at initial consultation

- % of key symptoms and signs checked and diagnostic tests performed by HCWs
- Distribution of final diagnoses (including their severity) made by HCWs
- Concordance between treatment prescribed and final diagnoses made by HCWs
- Concordance between final diagnoses as proposed by ePOCT+ and final diagnoses by HCW (*intervention HFs only*)

Definitions used for the outcome measures and indicators of objective 1

- Clinical cure is a positive answer to the question “Is the child cured?” OR “Has the child improved?” (if not cured) asked to caregiver through a phone call (or home visit) at day 7. Non-referred secondary hospitalizations (see definition below) will however be considered as clinical failures even if the child is already cured at day 7.
- Initial consultation is the first visit of a sick child for an acute problem at a HF participating in the study (and thus registered electronically); timeframe from completion of the initial visit up to midnight of the same day.
- Re-attendance visit is a consultation (not necessarily at a HF participating in the study) taking place from the day after initial consultation up to day 7 included. A re-attendance visit can be scheduled (proposed by the HCW on a certain day) or unscheduled (upon decision by caregivers).

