- Primary referral is a decision of referring the child to hospital taken by the HCW at the initial consultation - Secondary referral is a decision of referring the child to hospital taken by the HCW during a re-attendance visit taking place from the day after initial consultation up to day 7 included.
- Primary hospitalization is an admission to a hospital ward taking place the same day as the initial consultation
- Secondary hospitalization is an admission to a hospital ward taking place from the day after initial consultation up to the phone call at day 7 included. A non-referred secondary hospitalization is a direct visit to hospital without a re-attendance visit the same day at a HF participating in the study.
- Antibiotic prescription is any oral, intramuscular or intravenous (but not topical) antibiotic prescribed by a HCW during the initial consultation or a re-attendance visit
- Antimalarial prescription is any oral, rectal, intramuscular or intravenous antimalarial prescribed by a HCW during the initial consultation or a re-attendance visit
- Febrile child is a child with a history of fever and/or a high temperature
- Malaria testing is a malaria RDT or microscopy ordered by a HCW during an outpatient visit
- Day 7 is a range of 6-14 days post initial consultation to allow for completion of home visit for children whose caregiver reports having no phone / no phone number.

Additional longitudinal analyses:

- Change in % of children prescribed an antibiotic over time
- Change in % of children with basic anthropometrics and clinical signs measured over time (intervention arm only)
- Change in % of consultations where ePOCT+ was used over time (intervention arm only)

7.2 Indicators for Objective 2: Improve the algorithm and adapt it to spatiotemporal variations

- Number of positive impact modifications in the algorithm identified by ML-based analyses
- Number of positive impact modifications tested through randomized sub-studies
- % of these positive impact modifications confirmed to be safe and useful by randomized sub-studies
- Number of modifications implemented by type of impact (better clinical cure, less severe clinical outcomes, less medicines or diagnostic tests needed, shorter consultation time...)

Definitions used for the indicators of objective 2

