8.1.3 Re-attendance visits in case of persisting or worsening of symptoms

At initial consultation, the advice to caregivers on when to bring the child back to the HF is left at the discretion of the HCW. In intervention facilities, HCWs will be guided by the ePOCT+ tool, which recommends conditional follow-up based on WHO and national guidelines.

At re-attendance visits, whether scheduled or unscheduled, children will be managed according to the study arm to which they were initially assigned (ePOCT+ or routine care) in Phase 1, and with the support of ePOCT+ for all children in Phase 2. In case children still present fever at day 7, the algorithm will recommend in all cases to give an antibiotic to cover the possibility of an undetected bacterial infection. If surveillance laboratory results show that the child was suffering from a rare bacterial infection not covered by the antibiotic provided at day 7 (e.g. rickettsiosis or leptospirosis), the caretakers will be contacted to ensure that the child is indeed cured. If the child is still or again sick, caretakers will be asked to bring the child to the health facility to be assessed clinically and receive the necessary specific antibiotic.

If the child comes back to the same HF as for the initial consultation, the HCW will have access to the electronic data of that initial consultation that is saved in the HF tablets. If the child goes to a different HF that is participating to the study, the HCW will not have access to that data. Investigators will however be able to link data collected at different facilities (as long as they are part of the study) for a same child through the unique identification number provided to caregivers. If the child goes to a HF not participating in the study, no data will be available for that consultation. The ePOCT+ registration module, used at all participating facilities, will inquire about the type of visit (initial / scheduled re-attendance / unscheduled re-attendance) and the main reason for that visit.

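### A secondary admission that follows a same-day return to a study facility is neither a clinical failure nor a severe outcome if the child has improved by the day-7 contact

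*Protocol*

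**What the plan says.** Protocol 7.1 builds the safety comparison from four definitions.

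- **Cure.** "Clinical cure is a positive answer to the question" whether the child is cured or, failing that, has improved. The caregiver is asked by phone or at a home visit.
- **Contact window.** "Day 7 is a range of 6-14 days post initial consultation".
- **Override.** Non-referred secondary hospitalizations "will however be considered as clinical failures even if the child is already cured at day 7". No other admission overrides the caregiver's answer.
- **Non-referred.** "A non-referred secondary hospitalization is a direct visit to hospital without a re-attendance visit the same day at a HF participating in the study". The test is where the child was seen that day. A referral decision is not part of it.

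Beside death, the severe outcome is the percentage "of children with non-referred secondary hospitalization by day 7". The section also states that "Secondary referral is a decision of referring the child to hospital taken by the HCW during a re-attendance visit", but no listed outcome uses that term. The measure of completed hospitalization among referred children sits under primary referrals.

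On the route to admission, Protocol 8.1.3 leaves return advice to the health worker and adds: "In intervention facilities, HCWs will be guided by the ePOCT+ tool, which recommends conditional follow-up". Section 6.1 has ePOCT+ used again at re-attendance and has it guide the choice between referral and home treatment.

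The raw information is collected. The synopsis describes a day-7 questionnaire "asking if the child is still sick, was hospitalized secondarily, or died".

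**The concern.** Phase 1 asks whether antibiotic use can be cut without harm. Non-inferiority on cure carries the safety claim, and the antibiotic comparison is tested only if it is met (10.1.1, 10.3). An admission after deterioration is a plain signal of harm. Under these definitions, whether it counts depends on the path the child took to hospital, which is behaviour after randomization that the intervention may influence. If more deteriorating children in the ePOCT+ arm return to the study facility first, more of that arm's admissions go uncounted, and the comparison could understate a rise in admissions.

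The protocol is also uneven in its own usage. Section 8.2 describes severe disease as leading to secondary hospitalization or death, with no condition on route. Section 12.2 expects fewer secondary admissions, but no outcome listed in 7.1 measures their total, so neither that benefit nor its opposite can be seen.

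**Working it through.** **Step 1: classify the possible courses under 7.1, read literally.**

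| Course after the initial visit | Clinical outcome | Severe outcome |
|---|---|---|
| Goes directly to hospital, admitted, improved at contact | Failure | Yes |
| Returns to a participating facility, admitted same day, cured or improved at contact | **Cure** | **None** |
| Same route, not improved at contact | Failure | None |
| Same route, dies | Not a cure | Yes (death) |
| Returns one day, admitted a later day with no visit that day | Failure | Yes |
| Admitted via a non-participating facility | Failure | Yes |
| Referred at the initial visit, admitted the next day | Failure | Yes |

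The gap is the second row. The last row works in the other direction: it would count against an arm that refers more at the initial visit.

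**Step 2: reproduce the plan's own figure, to fix the scale.** Inputs from 10.1.1: control failure 3%, margin 0.9 points (risk ratio 1.3), one-sided alpha 0.025, power 80%, cluster size 900, intraclass correlation 0.002.

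- n per arm = (1.960 + 0.842)² × 2 × 0.03 × 0.97 / 0.009² = 5,640
- Design effect = 1 + 899 × 0.002 = 2.798
- Clusters = 5,640 × 2.798 / 900 = 17.53. Adding one cluster per arm gives 18.53, rounded up to 19.
- 19 × 900 = 17,100 per arm, and 34,200 × 1.10 = 37,620

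This matches the protocol and is not in dispute.

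**Step 3: illustrate the mechanism.** The documents give no secondary admission rates (s) and no share arriving through a same-day return (r), so both are assumed. All children on that route are taken as cured or improved at contact, which makes the effect an upper bound. Counted control failures are held at 3.0%, and failures other than non-referred admissions (b) are equal in both arms.

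- Non-referred admissions = s × (1 − r)
- b = 3.0% − s_control × (1 − r_control)
- Counted risk ratio = [b + s_ePOCT+ × (1 − r_ePOCT+)] / 3.0%
- All-admissions risk ratio = (b + s_ePOCT+) / (b + s_control)
- Chance of passing (counted outcome, 0.9-point margin, 19 clusters per arm) = Φ[(0.009 − difference)/SE − 1.96], with SE from an effective size of 17,100 / 2.798 ≈ 6,112 per arm

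Worked line for 1.0% vs 1.5% with shares 30% vs 70%: non-referred 1.0 × 0.7 = 0.70% and 1.5 × 0.3 = 0.45%; b = 2.30%; counted failures 3.00% and 2.75%, ratio 0.92; all admissions (2.30 + 1.5) / (2.30 + 1.0) = 3.80 / 3.30 = 1.15.

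In each pair below, control comes first.

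| Admissions | Route share | Non-referred | Counted RR | All-admissions RR | Chance of passing |
|---|---|---|---|---|---|
| 1.0%, 1.5% | 30%, 30% | 0.70%, 1.05% | 1.12 | 1.15 | 41% |
| 1.0%, 1.5% | 30%, 50% | 0.70%, 0.75% | 1.02 | 1.15 | 78% |
| 1.0%, 1.5% | 30%, 70% | 0.70%, 0.45% | 0.92 | 1.15 | 97% |
| 0.5%, 0.6% | 30%, 30% | 0.35%, 0.42% | 1.02 | 1.03 | 76% |
| 0.5%, 0.6% | 30%, 70% | 0.35%, 0.18% | 0.94 | 1.03 | 94% |

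**Step 4: when does the sign reverse?** It reverses only if r_ePOCT+ > 1 − (s_control / s_ePOCT+) × (1 − r_control). For 1.0% vs 1.5%, that is 53.3% if the control share is 30%, and 66.7% if it is 50%. With equal shares there is no reversal; part of the rise is simply lost (1.12 instead of 1.15).

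**Step 5: how large must the uncounted part be to reach the margin?** If counted failures are equal at 3.0% and uncounted control admissions are q, the ePOCT+ arm needs 1.3 × (3.0 + q) − 3.0. That is 1.03% for q = 0.1% and 1.55% for q = 0.5%.

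**The case against.** The exclusion is explicit and can be defended. A child who comes back, is recognised as sick and is sent to hospital may show the system working, and scoring every such admission as a failure could penalise correct detection. That argues for leaving the primary definition alone. It does not argue against reporting the admissions.

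Unscheduled re-attendance at any facility is compared between arms, so part of the route is visible. That also stands, but the measure does not show admission and omits scheduled returns.

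Three stronger readings are tempting and are not supported:

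- A reader might infer that ePOCT+ steers children into the uncounted route. Section 8.1.3 leaves return advice to the health worker and bases the tool's advice on WHO and national guidelines. Section 8.1.6 gives control facilities IMCI and national guidelines too, and 12.2 expects fewer re-attendances. A route difference is plausible but undocumented.
- A reader might infer that the comparison will favour ePOCT+ while admissions rise. That needs the sizeable route difference in step 4, and the day-0 referral case can act the other way.
- A reader might infer that scale-up hangs on this result. Section 3.2 plans the extension outright, and 8.1.1 promises control facilities the intervention within a year.

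Finally, Protocol 10.3 defers detail to a statistical analysis plan. The SAP supplied covers only the medAL-mentor study and cites a separate Phase 1 SAP (5.2.1). A suitable sensitivity analysis may exist there.

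**Conclusion.** The gap follows from the definitions and needs no assumption: a child admitted on the day of a return visit to a participating facility, and cured or improved at the contact, is a clinical cure with no severe outcome. It is limited to that group as far as cure is concerned.

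Its effect on the arm comparison cannot be sized from the documents. Under the assumed rates, the counted risk ratio ranges from 0.92 to 1.12 for the same rise in admissions from 1.0% to 1.5%, depending only on the route shares. A breach of the 1.3 margin that goes wholly unseen would need roughly 1.0% to 1.6% uncounted admissions in the ePOCT+ arm, against 0.1% to 0.5% in control. This is a worthwhile and inexpensive correction to the outcome list. It is not evidence that the non-inferiority result would be wrong.

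**What to change.** Keep the primary definition. Then:

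1. Add to the Phase 1 severe outcomes in 7.1 the percentage of children with any secondary hospitalization by day 7, with or without a same-day re-attendance, reported by arm.
2. Pre-specify a sensitivity analysis of the cure co-primary in which every secondary hospitalization not following a day-0 referral is a failure. The day-0 exception avoids penalising an arm that refers more at the first visit.
3. Report both alongside the non-inferiority result.
4. Check the Phase 1 SAP first, and align it with the protocol if it already covers this.

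The cost is protocol and SAP wording, one extra table and one extra analysis. No new data are needed: secondary hospitalization is already asked at day 7, referral decisions at re-attendance are already recorded (synopsis), and visits to study facilities can be linked by the identification number (8.1.3). The downside is that the added measure may count some appropriate re-referrals as events, which is why it belongs beside the primary outcome and not in its place.
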